4.3 Exploratory Objective(s) & Endpoint(s)

Exploratory objectives

Part A:

- To evaluate single cell expression patterns of skin biopsies of affected and non-affected skin with TOFA therapy
- To examine changes in interferon α/γ receptor, STAT phosphorylation patterns with TOFA therapy using immunohistochemistry
- To investigate mRNA expression patterns in peripheral blood upon treatment with TOFA with focus on interferon regulated genes

Parts B and C:

- To evaluate steroid sparing properties of TOFA for SLE-CL
- To evaluate TOFA effect of overall disease activity in SLE as measured by the SLEDAI and BILAG
- To evaluate effects of TOFA on quality of life as measured by the Skindex (appendix 4) and overall well-being

Exploratory endpoints at week 4, 8, 12, 24, 52, and 76

Part A: Pharmacodynamics (PD)

- PD parameters include assessment of inhibitory effect of TOFA on expression of IL-2 responsive target genes downstream of the JAK/STAT pathway, such as FOXP3, SOCS3, IL-2R α , interferon - γ and granzyme B.

Parts B and C:

- Decrease of absolute dose of systemic CS from baseline
- Decrease of body weight adjusted CS dose from baseline
 - CS dosing is measured in prednisone-equivalents
- Proportion of subjects who discontinue systemic CS
- Proportion of subjects with cutaneous relapse
- Change of BILAG score from baseline¹³
- Absolute value and percent change in plasma: Complement C3 and C4d, autoantibodies (anti-dsDNA)
- Change in number of inflamed joints from baseline¹⁴
- Change in SKINDEX score from baseline¹⁵
- Change of CLASI damage score¹⁶ from baseline
- Change in SLEDAI score at each time point
- Change in protein: creatinine ratio at each time point.
- Change in subject's overall well-being at each time point
- Change in subject's ESR
- Proportion of subjects with clinically important reduction in SLE activity at each time point, based on CRV changes compared to baseline
- Proportion of subjects with flare of SLE activity at each time point, as defined by the BILAG¹⁷

Data of subjects who enter Part B before week 8 and/or Part C before week 24 will be considered on a last-observation (LOC) carried forward basis for endpoints of Part A and B, respectively.

5. Study Participants

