6.2 Dosing

TOFA dosing: Twice daily orally

As documented in the TOFA Investigator brochure (Section 6.1; Version March 2016) doses up to 30 mg twice daily were safe and tolerated. However, for the purpose of this study only the dose of TOFA approved for rheumatoid arthritis (5 mg PO BID) will be tested.

Based on TOFA PK in the Rheumatoid Arthritis (RA) population [body weight (BW) ranging from 40 kg - 140 kg)], clearance (CL) of TOFA is not dependent on body weight in adult subjects. Thus, the starting dose of TOFA will be 5 mg orally twice daily, an approved dose of TOFA in adult RA subjects in most countries. Dose escalation will not occur even with lack of SLE-CL improvement.

Corticosteroids (CS):

At study entry, CS dosage must be \leq 20mg/day. CS should be kept stable up to and including week 4.

CS can be decreased starting week 5:

- CS may be decreased for improvement of the CLASI activity score by \geq 50% from baseline and must be tapered for CLASI activity scores of 0 for $>$ 8 weeks (or 2 subsequent study visits, whatever is shorter), provided CS are mainly prescribed for SLE-CL. This will minimize morbidity associated with CS use as much as possible.
- If CS are mainly prescribed for other SLE manifestations besides SLE-CL, then CS can be decreased as per the investigator's decision, even in the setting of complete response of SLE-CL, based on continued improvement of clinical findings of SLE.

Oral CS may be increased above the baseline level up to max of 60 mg/day for new BILAG A or B flares in organ systems other than mucocutaneous organ system (i.e. neurologic, ophthalmologic, musculoskeletal, cardiopulmonary, gastrointestinal, renal, hematological organ systems) but must be returned to baseline dose or lower within 14 days. If this is not achieved then the subject is considered a treatment failure.

- Up to 3 doses of pulse methylprednisolone may be given for new BILAG A or B flares instead.
- CS increases can occur no more than 3 times during the duration of the study, Part A- C.
- Subjects requiring more than 3 CS increases will be withdrawn from treatment phase of study.

Other anti-inflammatory medications used as part of standard of care (SOC) for SLE

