8.3 Effectiveness Analyses

Due to the small sample size, results may not show statistical significance. Statistical significance may not be reached in final data analysis. However, a trend towards improved clinical status may assist planning efforts of a larger clinical trial to assess efficacy.

The efficacy population will be all subjects who were enrolled in the study and received at least 1 dose of TOFA. No interim analyses are planned. We will perform intention-to-treat analyses, with the last observation carried forward in primary analyses; and will also perform analyses on observed data in secondary analyses. As this is an open-label study, no control group is available. Efficacy measures are listed under Section 7. Data of subjects who enter Part B before week 8 and/or Part C before week 24 will be

considered on a last-observation (LOC) carried forward basis for endpoints of Part A and B, respectively.

To assess the benefits of TOFA on skin manifestations of SLE, we will use descriptive analysis and contingency table analysis, using Chi-square and Fisher Exact test as appropriate, to determine the proportion of subjects who are partial or complete CLASI responders at weeks 4, 8 and 24 compared to baseline. To assess the effect of TOFA on skin damage, we will compare the change (increase) of CLASI damage score¹⁶ from baseline to the end of Part B and C, respectively, using paired T-tests.

To assess the steroid –sparing properties of TOFA, we will determine the proportion of study subjects who can discontinue steroids at the end of Part B and C, respectively. We will also evaluate steroid sparing properties of TOFA for SLE-CL by comparing steroid doses (absolute and weight-adjusted) at baseline with those in the end of Part B and C, using a paired T-test.

Similarly, we will assess TOFA effect of overall disease activity in SLE as measured by the numeric SLEDAI and BILAG scores, respectively. We will also perform sub-analyses and evaluate improvement or resolution of other organ-system activity (e.g. serological activity – measured by anti-dsDNA antibodies and low complement levels; joint counts) using paired T-tests and contingency table analysis, as appropriate. In a similar fashion the change of the other SLE core response variables (CRV) besides disease activity (SLEDAI, BILAG) will be assessed at each study visit.

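### Steroid sparing is read from doses at fixed time points, so permitted rescue courses can fall between assessments and a subject with equal or higher total exposure can be reported as spared

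*Combined protocol and SAP*

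**What the plan says.** All references are to the combined protocol and SAP.

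- **Analysis.** Section 8.3 assesses steroid sparing in two ways. One is a test of dose: "comparing steroid doses (absolute and weight-adjusted) at baseline with those in the end of Part B and C, using a paired T-test". The other is a status: "we will determine the proportion of study subjects who can discontinue steroids at the end of Part B and C, respectively".
- **Endpoints.** Section 4.3 words the dose endpoint as "Decrease of absolute dose of systemic CS from baseline", with a weight-adjusted version, both in prednisone-equivalents. The time points come under the title "Exploratory endpoints at week 4, 8, 12, 24, 52, and 76".
- **Permitted rescue.** Section 6.2 states: "Oral CS may be increased above the baseline level up to max of 60 mg/day for new BILAG A or B flares". The flares must be in organ systems other than the mucocutaneous one, and the dose "must be returned to baseline dose or lower within 14 days". As an alternative, "Up to 3 doses of pulse methylprednisolone may be given for new BILAG A or B flares instead"; no milligram amount is given. The cap is "CS increases can occur no more than 3 times during the duration of the study", which Section 6.2 applies across Parts A to C.
- **What is absent.** Sections 4.3 and 8.3 and the data analysis plan in Appendix 3 (part J) contain no cumulative or time-averaged CS dose, no count of rescue courses, and no rule for a dose recorded during or soon after rescue.

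**The concern.** The endpoint is the dose of systemic CS, with no split by indication and no exclusion of rescue. A dose recorded at a visit says nothing about a short course that began and ended since the last visit. After week 12, Part B visits are 4 weeks (28 days) apart and Part C visits 8 weeks (56 days) apart (Section 7.1). The listed CS endpoint times after week 24 are only weeks 52 and 76. A course of 14 days or less fits inside any of these gaps.

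Under Section 6.5, the rescue criterion for treatment failure is rescue beyond the allowance. A subject rescued within it can therefore stay in the analysis with the later, lower dose and count as a dose reduction, or as off CS, with no mention of the rescue. There is no control group to show how much rescue would have been expected anyway, and Section 8.3 intends the trends to inform a larger trial.

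**Working it through.** The plan gives no figure to reproduce: there is no sample size calculation and no expected CS dose or rescue rate. The check is exposure arithmetic.

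**Inputs from the documents:** rescue up to 60 mg/day, 14 days, at most three increases over Parts A to C (6.2); entry dose at most 20 mg/day (5.1); end of Part B at week 24 = 168 days; end of Part C at week 76 = 532 days.

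**Assumptions:** baseline 10 mg/day; taper to 7.5 mg/day from day 36; each course lasts 14 days and returns to 7.5 mg/day. A course is either a linear fall from 60 to 7.5 mg (mean 33.75 mg/day) or 60 mg/day throughout (upper bound). Pulses are left out because no dose is stated.

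**Excess per course** = 14 x (mean rescue dose - 7.5)
- Linear: 14 x 26.25 = 367.5 mg
- Flat: 14 x 52.5 = 735 mg

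**To week 24**
- Unchanged: 10 x 168 = 1680 mg
- Taper only: 10 x 35 + 7.5 x 133 = 1347.5 mg (-19.8%), a saving of 332.5 mg
- One linear course: 1347.5 + 367.5 = 1715 mg (+2.1%)
- One flat course: 1347.5 + 735 = 2082.5 mg (+24.0%)

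**To week 76**
- Unchanged: 10 x 532 = 5320 mg
- Taper only: 5320 - 2.5 x 497 = 4077.5 mg (-23.4%)
- Three linear courses: 4077.5 + 1102.5 = 5180 mg (-2.6%)
- Three flat courses: 4077.5 + 2205 = 6282.5 mg (+18.1%)

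Unless a course is in progress at the visit, the end-of-part dose reads 7.5 against 10 mg/day, that is -25%, in every row.

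**Off-CS status.** Baseline 10 mg/day, one full course at 60 mg/day, then off CS from week 16 (day 112): 14 x 60 + 10 x 98 = 1820 mg by week 24, against 1680 mg unchanged (+140 mg). With half that excess (14 x 50 / 2 = 350 mg less) the total is 1470 mg, a net saving of 210 mg. Both subjects count as discontinued.

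**When rescue outweighs the taper.** In the 24-week example, the average number of courses per subject at which group exposure equals baseline exposure is 332.5 / 367.5 = 0.90 (linear) or 332.5 / 735 = 0.45 (flat). The plan gives no rescue frequency to set against these.

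**Timing and the mean.** If one flat course were equally likely to fall at any time in the 168 days, the chance of its being in progress on a given day would be about 14 / 168 = 8.3%. The expected excess in a spot dose would then be 52.5 x 14 / 168 = 4.4 mg/day, the same as the excess in the period average, 735 / 168 = 4.4 mg/day. Under that assumption the group mean is not pushed one way by missed courses, but about nine rescued subjects in ten would show no trace of the rescue.

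**The case against.** The strongest reply is that the objective in Sections 4.3 and 8.3 is sparing for SLE-CL, while Section 6.2 limits rescue to flares outside the mucocutaneous system. On that view the maintenance dose at the end of a part is the right measure, and non-skin rescue answers another question. This stands as a reason to keep the planned comparison. It does not remove the point, because the endpoint is worded as total systemic CS and rescue is not excluded.

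Four stronger readings are tempting, and the documents do not support them.

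- *The rescue rule hides rescue by design.* Nothing keeps a course away from weeks 24 or 76. A course in progress at a visit raises the recorded dose and works against sparing.
- *The mean is biased toward sparing.* That needs a rescue frequency and timing which the plan does not state.
- *Three courses by week 24 show the size of the problem.* Loading all three into 24 weeks would give 2450 to 3552.5 mg (+46% to +111%). That timing is not forbidden, but the allowance is set over 76 weeks, where the same subject ends at -2.6% to +18%.
- *The planned measure should be replaced.* Section 5.2 excludes a CS increase within 2 weeks and i.v. CS within 4 weeks before Trial Day 1, so baseline is largely free of bursts. An on-study average that includes bursts is not like-for-like with it, and an average from Trial Day 1 also includes the weeks of required stable dosing.

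Section 6.5 may also remove some rescued subjects. It makes an increase in background therapy for non-renal SLE a treatment failure, and Section 6.1 lists oral CS among background therapies, yet Section 6.2 permits increases for several non-renal flares. Renal rescue is untouched by that criterion. For a discontinued subject, last observation carried forward keeps the last dose, possibly a raised one.

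**Conclusion.** The point holds at subject level. As written, the steroid-sparing analysis can report a subject as spared, or as having discontinued CS, when total systemic CS exposure was equal to or above that of staying on the baseline dose. In the worked example a 25% reduction is read while exposure is +2% to +24% (one course by week 24) or -2.6% to +18% (three courses over 76 weeks). These figures rest on the assumed 10 mg/day baseline, the taper to 7.5 mg/day from day 36 and full 14-day courses. Higher exposure is not automatic: it needs near-maximal courses, or a small or late taper. The direction and size of any effect on the group mean cannot be determined from the documents.

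This is a cheap improvement on an exploratory endpoint in an uncontrolled study of 20 subjects whose primary objectives are PK and safety.

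**What to change.** In Section 8.3, keep the end-of-part comparison and add:

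1. Average daily prednisone-equivalent systemic CS dose for Trial Day 1 to week 24 and for week 24 to week 76, with and without rescue courses and pulses.
2. The number of subjects rescued and the number of courses, per period.
3. A rule that a subject counts as having discontinued CS only if no rescue CS was given in a pre-specified window before the visit.
4. A sentence stating that baseline is largely burst-free by eligibility and that rescue is for non-skin flares, so the with-rescue figure measures total systemic CS sparing.

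Sections 6.2 and 6.5 must also be reconciled on CS increases for non-renal flares, because this decides which rescued subjects remain in the analysis.

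The cost is a derived variable, a short table and a few lines of text; no visit or treatment rule changes for items 1 to 4. One check is needed first. The schedule in Section 10 shows concomitant medications at each visit but does not say that CS dose and start and stop dates are captured, so confirm that the form does so. The with-rescue figure may be less favourable than the planned one.

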Background/Purpose: Tofacitinib is an oral Janus kinase inhibitor that is being investigated for juvenile idiopathic arthritis (JIA). Here, we report the pharmacokinetics (PK), safety, and taste acceptability of tofacitinib following multiple oral doses in patients (pts) 2–<18 years (yrs.) old with active JIA.

Methods: Data were obtained from an open-label, non-randomized, multicenter, Phase I study (NCT01513902) where JIA pts were given 5 mg adult equivalent (based on body weight) of tofacitinib (tablet or solution) twice daily (BID) for 5 days (Table). There were 3 cohorts (COH) based on pt age, COH1: 12–<18 yrs, COH2: 6–<12 yrs, and COH3: 2–<6 yrs, with a target enrollment per group of ≥ 8 JIA pts for $N = \geq 24$ evaluable pts completing the study. Pts were enrolled in a stepwise approach beginning with the older age COH first. Subsequent younger age COH were enrolled following confirmation of safety and PK from the previous COH. PK parameters of tofacitinib were calculated using non-compartmental analysis of plasma concentration (conc)-time data. Taste acceptability of the solution formulation was listed and categorically summarized (frequency and %).

Results: 26 pts (COH1 [N=8], COH2 [N=9], and COH3 [N=9]) were included in this analysis. Pts' age ranged from 2–17 years; all were white except for one; there were 17 females and 9 males. Baseline disease characteristics were similar across all COH. All exposure metrics including geometric mean (GM) area under the conc-time curves (AUC), maximum (C_{max}), minimum (C_{min}) and predose (C₀) conc were lower in COH2 relative to those in COH1; however, due to higher doses in COH3 (modified after interim analysis of COH1 and 2), the mean AUC in COH3 was comparable to COH1. GM apparent volume of distribution (V/F) decreased with age (COH1=104.9 L, COH2=71.0 L, COH3=51.4 L). Average terminal half-lives (t_{1/2}) were COH1=2.62 h, COH2=1.95 h, and COH3=1.77 h. GM tofacitinib CL/F were 53%, 39%, and 11% higher in COH1, COH2, and COH3 pts, respectively, vs adult RA pts (18.4 L/h) receiving tofacitinib 5 mg BID. GM CL/F and V/F parameters were similar between males and females. Tofacitinib, administered over 5 days as multiple dose tablets or solution formulation, was well tolerated and taste for the solution formulation was found acceptable in children with active JIA. No serious adverse events or new safety signals were identified.

Conclusion: PK results from this study established dosing regimens for pts aged ≥ 2 years to be used in the upcoming efficacy and safety studies of tofacitinib in JIA pts. Tofacitinib was well tolerated in this study in JIA pts. Overall, pts found the taste of the tofacitinib solution formulation to be acceptable.

APPENDIX 2. Moderate or Potent CYP3A Inhibitors and Inducers

NOTE: Topical administration (e.g., cutaneous, ophthalmic, or intravaginal) of listed concomitant medications, which are prohibited if administered systemically, is allowed in the study.
	
Moderate or Potent CYP3A Inhibitors	Moderate or Potent CYP3A Inducers
HIV antivirals:	efavirenz (Sustiva)
-delavirdine (Rescriptor)	nevirapine (Viramune)
-indinavir (Crixivan)	Barbiturates
-nelfinavir (Viracept)	carbamazepine (Carbatrol, Tegretol)
-ritonavir (Kaletra, Norvir)	modafinil (Provigil)
-saquinavir (Fortovase)	phenobarbital
-atazanavir	phenytoin (Dilantin, Phenytek)
amiodarone (Cordarone, Pacerone)*	rifabutin (Mycobutin)
cimetidine (Tagamet)	rifampin (Rifadin, Rifamate, Rifater)
clarithromycin (Biaxin, Prevpac)	rifapentine (Priftin)
telithromycin (Ketek)	St. John's Wort
clotrimazole	troglitazone (Rezulin)
chloramphenicol	All Investigational Drugs
diethyl-dithiocarbamate	DMARDs
diltiazem (Cardizem, Tiazac)	All Biologics** , such as: anakinra (Kineret), etanercept (Enbrel), adalimumab (Humira), infliximab (Remicade), abatacept (Orencia), canakinumab (Ilaris), tocilizumab (Actemra), golimumab (Simponi), rituximab (Rituxan),
erythromycin	
fluconazole (Diflucan)	
fluvoxamine (Luvox)	
Grapefruit juice and marmalade	
itraconazole (Sporanox)	
ketoconazole (Nizoral)	Other DMARDs**: leflunomide, sulfasalazine, d-penicillamine, bucillamine, mizoribin, azathioprine, cyclosporine, tacrolimus, auranofin, aurothioglucose, aurothiomalate, staphylococcal protein A immuno-absorbant pheresis columns
mifepristone (Mifeprex, RU486)	
nefazodone (Serzone)	
norfloxacin (Shibroxin, Noroxin)	
mibefradil	
verapamil (Calan SR, Covera HS, Isoptin SR, Tarka, Verelan)	
voriconazole	

APPENDIX 3. Data Safety Monitoring Plan

DATA SAFETY MONITORING PLAN

**Tofacitinib for Systemic Lupus Erythematosus
With Cutaneous Lesions**

(IND 132786)

TABLE OF CONTENTS

A. SUMMARY OF THE PROTOCOL	38
B. BRIEF DESCRIPTION OF THE PROTOCOL (STUDY DESIGN)	39
C. INCLUSION/EXCLUSION CRITERIA	41
D. SAMPLE SIZE	44
E. TRIAL MANAGEMENT	44
F. TARGET POPULATION DISTRIBUTION (WOMEN, MINORITIES, ETC.)	45
G. INSTITUTIONAL REVIEW BOARD PROTOCOL REVIEW	45
H. DATA SAFETY AND MONITORING PROCEDURES	46
I. DATA MANAGEMENT	47
J. DATA ANALYSIS PLAN	50
K. REGULATORY ISSUES	50
L. RISKS & BENEFITS	51
M. PREMATURE CLOSURE OF STUDY	53
N. TRIAL EFFICACY	54

Since there are only 20 subjects, the PI will review all safety events that occur and no formal DSMB will be convened for this study.

A. SUMMARY OF THE PROTOCOL

This proposed study is an Investigator initiated clinical trial to study the safety and efficacy of *tofacitinib* (TOFA) for *systemic lupus erythematosus with cutaneous lesions* (SLE-CL). TOFA is approved under the brand name (XELJANZ) for the treatment of adult patients with moderate to severe rheumatoid arthritis (RA). Tofacitinib is also being developed for the treatment of psoriasis (oral and topical), Crohn's disease, ulcerative colitis, psoriatic arthritis, and ankylosing spondylitis and dry eye disease, and for the prevention of renal allograft rejection.

TOFA, a small molecule that inhibits Jak3, Jak1 and to a lesser degree Jak2, has been proven efficacious in RA in phase III trials. Notably, a series of Jak-STAT signalling cytokines, especially type I IFNs, IL-10 and IL-6, as well as the hormone prolactin, have been implicated in the pathogenesis of systemic lupus erythematosus (SLE). Such immunological abnormalities are thought to be even more pronounced among subjects with SLE onset early in life, i.e. with SLE diagnosis during childhood and adolescence (SLE). In this context, targeting the Jak-STAT pathway may be an attractive approach to manage inflammation and auto-immunity in SLE.

All type I IFN family members bind a common receptor complex (IFNAR1 and IFNAR2). Viral infection rapidly induces leukocyte production of IFN- α and - β , which initiates a JAK/STAT signaling cascade leading to transcription of target genes that promote host protection and viral elimination. IFN also promotes survival and differentiation of mature lymphocytes, class switching at immunoglobulin heavy chain loci, and activation of dendritic cells. The primary source of type I IFNs in the body is natural IFN-producing cells (NIPCs), also known as plasmacytoid dendritic cells (pDCs). Type I IFNs play a major role in the pathogenesis of SLE and have been shown to be associated with lupus-associated skin disease in murine studies

TOFA was efficacious in mouse models of skin inflammation induced by imiquimod application and IL-23 injection as assessed by clinical, histological and gene expression measures in the mouse ear. TOFA was also efficacious in a CD4+CD45RBhighCD25- T-cell transfer model that mimics aspects of psoriasis pathology and in a xenograft model where human psoriatic skin from psoriasis patients was transplanted onto severe combined immunodeficiency (SCID) mice. TOFA was efficacious in rodent and primate models of heterotopic heart transplantation and rodent models of arthritis by subcutaneous delivery in osmotic pumps (Changelian et al, 2003, Milici et al, 2008). Thus, TOFA shows promise in multiple models of autoimmunity and immune dysregulation.

Further, pDCs are actively recruited to inflammatory skin lesions of humans with SLE.

Additionally, blockage of interferon activity has been shown to ameliorate lupus skin disease.

To date, belimumab, hydroxychloroquine, chloroquine and quinacrine are approved for adults with *systemic lupus erythematosus (SLE)*. The latter three medications are approved also for cutaneous lupus without the system form of the disease, i.e. SLE. Despite these medications, chronic skin disease remains a major problem with SLE⁷. Given the severity of the disease, the unmet medical need, and the low number of available subjects in this specific population, it is judged acceptable to assess the safety, tolerability and PK as primary objectives; and efficacy as secondary objectives in an open-label manner.

B. BRIEF DESCRIPTION OF THE PROTOCOL (STUDY DESIGN)

This 76-week, 3-part, Phase 1b/2 study is intended to evaluate the pharmacological properties (pharmacokinetics and pharmacodynamics) of TOFA administrated to young adults with moderately to severely active inflammatory *SLE-CL*.

- **Part A** (up to week 8) requires stable background medications;
- **Part B** (up to week 24) allows for tapering of *corticosteroids (CS)*, *in the setting of significant clinical improvement of SLE-CL as defined by a decrease in Cutaneous Lupus Erythematosus Disease Area and Severity Index (CLASI) activity score by ≥50% from baseline*, and

Part C (until week 76) permits tapering of other background medications in subjects with clinical remission of SLE-CL (CLASI activity score=0). TOFA dosing is kept stable during Part C.

Primary Objective

Part A (Cohort 1):

- To evaluate the pharmacokinetic (PK) profiles of TOFA in young adults aged between 18 and including 45 years with SLE -CL who are on stable treatment for SLE

Part A (Cohort 1 and Cohort 2)

- To evaluate the safety and tolerability of TOFA in young adults with SLE -CL

Part B and C:

- To evaluate the safety and tolerability of TOFA in young adults with SLE -CL

Primary endpoints

Part A (Cohort 1 only):

- **Day 5:** AUC_{inf} and C_{max} of tofacitinib

Part B: At Week 24

- Nature, severity, and frequency of adverse events
- Incidence and severity of laboratory abnormalities

Key Secondary Objective(s) & Endpoint(s)

Secondary objectives

- To evaluate the efficacy of TOFA in young adults with SLE -CL

Secondary endpoint**Part A and B****Efficacy on SLE skin disease**

- Proportion of subjects who achieve a skin response (complete or partial response) as per the validated Cutaneous Lupus Erythematosus Disease Area and Severity Index (CLASI) at weeks 4, 8 and 24 compared to baseline¹⁶. Response (compared to baseline at TD1) is defined as follows:
 - *Complete response (CR)* : complete resolution of the inflammatory rash (CLASI activity score = 0);
 - *Partial response (PR)*: $\geq 20\%$ improvement of the CLASI activity score
 - *No response*: $< 20\%$ improvement or even worsening of the CLASI activity score (CLASI relapse)

Exploratory Objective(s) & Endpoint(s)**Exploratory objectives****Part A:**

- To evaluate single cell expression patterns of skin biopsies of affected and non-affected skin with TOFA therapy
- To examine changes in interferon α/γ receptor, STAT phosphorylation patterns with TOFA therapy using immunohistochemistry
- To investigate mRNA expression patterns in peripheral blood upon treatment with TOFA with focus on interferon regulated genes

Parts B and C:

- To evaluate steroid sparing properties of TOFA for SLE -CL
- To evaluate TOFA effect of overall disease activity in SLE
- To evaluate effects of TOFA on quality of life

Exploratory endpoints at week 4, 8, 12, 24, 52, and 76**Part A:**

- PD parameters include assessment of inhibitory effect of TOFA on expression of IL-2 responsive target genes downstream of the JAK/STAT pathway, such as FOXP3, SOCS3, IL-2R α , interferon (IFN)- γ and granzyme B.

Parts B and C:

- Decrease of absolute dose of systemic CS from baseline
- Decrease of body weight adjusted CS dose from baseline

- CS dosing is measured in prednisone-equivalents
- Proportion of subjects who discontinue systemic CS
- Proportion of subjects with cutaneous relapse
 - *Cutaneous relapse:* a new CLASI activity score ≥ 4 in those subjects who previously achieved CR of SLE -CL (CLASI = 0)
- Change of SLEDAI and BILAG score from baseline
- Absolute value and percent change in plasma: Complement C3, C4d, autoantibodies (anti-dsDNA)
- Change in number of inflamed joints from baseline¹⁴
- Change in SKINDEX score from baseline
- Change (increase) of CLASI damage score from baseline
- Change in the SLE core response variables (CRV) which include
 1. Change in SLEDAI score at each time point
 2. Change in protein: creatinine ratio at each time point.
 3. Change subject's overall well-being at each time point
